N	Number (typically refers to subjects)
NDA	New Drug Application
NSE	Neuron-specific enolase
NIAID	National Institute of Allergy and Infectious Diseases,
NIH	National Institutes of Health
NIRS	Near infrared spectroscopy
OCRA	Office of Clinical Research Affairs,
OHRP	Office for Human Research Protections
OHSR	Office for Human Subjects Research
ONSD	Optic Nerve Sheath Diameter
OR	Odds Ratio
ORA	Office of Regulatory Affairs,
PHI	Protected Health Information
PCV	Packed Cell Volume
PNGT	Per Naso-Gastric Tube
PO	Per Os (by mouth)
PR	Per Rectum
PRW	Paediatric Research Ward (Queen Elizabeth Central Hospital)
PI	Principal Investigator
PICU	Paediatric Intensive Care Unit
PK	Pharmacokinetics
QA	Quality Assurance
QECH	Queen Elizabeth Central Hospital
QC	Quality Control
RBC	Red Blood Cell
REDCap	Research Electronic Data Capture
SAE	Serious Adverse Event/Serious Adverse Experience
SMC	Safety Monitoring Committee
SOP	Standard Operating Procedure
SSL	Secure sockets layer
TBI	Traumatic Brain Injury
TNF	Tumor Necrosis Factor
UC	Usual care arm of the clinical trial
US	United States
VENT	Mechanical ventilation arm of the clinical trial
WHO	World Health Organization

PROTOCOL SUMMARY

Title:	Treating Brain Swelling in Pediatric Cerebral Malaria
Phase:	3
Population:	Malawian children aged 6 months to 12 years, with cerebral malaria and MRI evidence of increased brain volume (brain volume score ≥ 6). Total of 128 children.
Number of Sites:	Single site: Paediatric Research Ward, Queen Elizabeth Central Hospital, Blantyre Malawi
Study Duration:	Six years participant accrual; one-year data analysis
Subject Participation Duration:	55 weeks: duration of hospital stay, and follow-up visits at 1, 6, and 12-months post-randomization.
Description of Agent or Intervention:	
Arm 1: Usual care + immediate ventilatory support for a maximum of 7 days. Brain death or death will be considered a failure of the primary intervention.
 
Arm 2: Usual care + infusion of 3% hypertonic saline to achieve a blood sodium concentration of 150-160 mmol/L. Ventilatory support will be provided to patients who experience a respiratory arrest, and this will be considered a failure of the primary intervention.
 
Arm 3: Usual care (elevation of the head of the bed 30 degrees and intravenous antimalarial drugs). Ventilatory support will be provided to patients who experience a respiratory arrest, and this will be considered a failure of the primary intervention.
 
Final outcomes will be determined at 7 days post-randomization: The primary study outcome will be recovery vs treatment failure, where treatment failure is a composite of death, ventilatory rescue (Arms 2 and 3), and brain death

Objectives:

Primary Objective

Compare final outcomes in pediatric CM patients receiving usual care (Arm 3) with both of two interventions (Arm 1 and Arm 2).

Secondary Objectives:

[figure not shown]
1. Among survivors of this interventional study, compare rates of adverse neurological outcomes in those assigned to the two interventions and those assigned to usual care.
2. Among all children admitted to the Paediatric Research Ward and screened for eligibility for randomization, evaluate and validate biomarkers of increased brain volume.
3. Assess the safety of early mechanical ventilation as well as intravenous hypertonic saline in children with CM.
4. Establish association between specific pathogenic mechanisms and TCD-derived phenotypes.

Description of Study Design:

Prospective, randomized, controlled non-blinded clinical trial

Estimated Time to Complete Enrollment:

Six years

PICU¹: will be on continuous monitoring 24hrs, then transferred to PRW

²pts in Arms 2 and 3 who experience respiratory arrest will be placed on ventilators.

³Treatment failure is a composite of death, ventilatory rescue or brain death

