Using malarial retinopathy to identify the high risk group: Recognizing the importance of being able to scale up the findings of this study, and appreciating the operational difficulties of identifying patients with malarial retinopathy, children with retinopathy-negative CM will also be enrolled and randomized to one of the three study arms. Randomization for the retinopathy-positive patients will be carried out independently of randomization for the retinopathy-negative patients. Should the clinical trial results reveal a positive therapeutic effect of either intervention (Arm 1 or Arm 2), uptake of study results across Africa will be enhanced if treatment decisions do not depend on the results of an ocular funduscopic examination, which requires expensive equipment and extensive training. This trial represents an opportunity to assess efficacy in the entire CM population (combined retinopathy-positive and retinopathy-negative). If efficacy can be demonstrated in the entire CM population, scalability will be enhanced, as indirect ophthalmoscopy will not be necessary before instituting an intervention which will have been shown to be beneficial.

Using MRI to identify the high-risk group: The data driving this study were collected using the 0.35T MRI in Malawi⁵². Evidence of severely increased brain volume is readily discernible via MRI, but clinically reliable surrogate markers of increased brain volume have yet to be identified. A secondary outcome of this study will be an evaluation of these potential surrogate markers so that, if a successful intervention is identified, its implementation will not require MRI technology to identify subjects at high risk of death.

During the first enrollment season (January-June 2018) 57 participants had MRI images interpreted in real time by a single neuroradiologist. When the season was completed, all images were independently re-interpreted by two different neuroradiologists. If there was a discrepancy in the assigned brain volume scores determined by the radiologists interpreting the images post-season, a consensus score was obtained.

Comparisons between the brain volume scores assigned in real time and the consensus score revealed an inability for neuroradiologists to differentiate a score of 6 or 7 in real time, leading to non-differential misclassification. Four subjects who had real-time assignment of brain volume

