Concurrent with our clinical trial, we will test and validate other surrogate measures of increased brain volume, an approach that is gaining ground in more sophisticated intensive care settings¹⁹⁵. These can all be carried out at the bedside and include optic nerve sheath diameter (ONSD) by ultrasound, cerebral flow velocities by transcranial Doppler ultrasound, NIRS monitoring of both cerebral oxygenation and skeletal muscle reperfusion dynamics, heart rate variability from the EKG, and clinical neurological examination.

Ultrasound measures of the optic nerve sheath diameter (ONSD): The optic nerve sheath is continuous with the dura mater of the brain and expands in the presence of raised ICP. The distention can be measured non-invasively by ultrasound. Several studies suggest that ONSD has potential as a screening test for elevated ICP¹⁹⁶⁻²⁰⁰. ONSD was a sensitive and specific predictor of CT scan signs of raised ICP and was elevated in 25 of 27 children with papilledema^{201, 202}. A small study in Uganda found increased ONSD in all patients meeting a broad case definition of CM²⁰³. We used this approach on the Research Ward in two different studies, and serial data have been collected on all patients since 2013, providing reassurance that this approach is feasible.

Ultrasound measures of the cerebral blood flow velocities: In both adults and children TCD-derived parameters have been shown to have utility to non-invasively estimate an absolute value for ICP²⁰⁴⁻²⁰⁶. As ICP rises, distal resistance to cerebral flow increases and results in a progressive reduction in diastolic flow velocity (Vd) and an increase in pulsatility index (PI= Systolic flow velocity-Vd / Mean flow velocity)²⁰⁷. In a prospective cohort of adult patients, Spearman correlation between Δ ICP measured invasively and changes to PI were averaged across time during induced ICP increase²⁰⁸. At the 0.05 level, baseline and plateau distributions of ICP and PI were significantly correlated ($r= 0.39 \pm 0.40$). In children with hydrocephalus, TCD has been shown to be a valid measure of ICP changes during cerebrospinal fluid drainage²⁰⁹⁻²¹¹. In 7 patients, TCD was performed with simultaneous invasive ICP measurement through a

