3 OBJECTIVES

3.1 Study Objectives

Primary Objective

Compare final outcomes in pediatric CM patients receiving usual care (Arm 3) with both of two interventions (Arm 1 and Arm 2).

Secondary Objectives:

1. Among survivors of this interventional study, compare rates of adverse neurological outcomes in those assigned to the two interventions and those assigned to usual care.
2. Among all children admitted to the PRW with CM whose parents consent to screening, evaluate and validate biomarkers of increased brain volume.
3. Assess the safety of early intubation and mechanical ventilation as well as intravenous hypertonic saline in children with CM.
4. Establish association between specific pathogenic mechanisms and TCD-derived phenotypes.
 - a. microvascular obstruction phenotype with MRI findings
 - b. hyperemia phenotype with hypercapnia on blood gas analysis, acidosis, and seizures on EEG
 - c. vasospasm phenotype with regional EEG findings of loss of fast frequencies and increased slow frequencies in territories of affected vessels and MRI findings with localized ischemic changes
 - d. low flow phenotype with compromised hemodynamics, diminished compensatory reserve and increased brain volume per MRI

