3.2.2 Secondary Outcome Measures

1. Neurological sequelae in survivors, assessed at 1, 6, and 12 months after randomization via the Malawi Developmental Assessment Tool (MDAT) for participants up to the age of 59 months old, and the Kaufman Assessment Battery for Children, Version II (KABC II) for participants over the age of 59 months. All survivors will also be assessed using the Glasgow Outcome Scale (GOS)²⁴⁷. The GOS is a global scale for functional outcome that rates patient status into one of five

categories: dead, vegetative state, severe disability, moderate disability or good recovery.

2. Surrogate measures of increased brain volume: At the time of admission (only): opening CSF pressure, archived samples of blood, urine and CSF. Daily while comatose: ophthalmoscopy for papilledema (present/absent), optic nerve sheath diameter in mm, NIRS measurements of cerebral oxygenation and muscle reperfusion, standardized neurologic observations.
3. Standard TCD phenotypes: microvascular obstruction, hyperemia, vasospasm, low flow, isolated posterior hyperemia). Potential mechanisms: increased brain volume per MRI/ischemic changes, hypercapnia/acidosis/seizures, localized ischemia on MRI, compromised hemodynamics/diminished compensatory reserve/increased brain volume per MRI

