Transcranial Doppler: TCD examination will be performed at enrollment and every 24 hours thereafter while the patient is hospitalized. Middle cerebral arteries (MCAs), extracranial internal carotid arteries (EC-ICAs), and basilar arteries (BAs) will be insonated at 1 mm intervals using the transtemporal or occipital acoustic windows. Systolic (Vs), diastolic (Vd), mean flow velocities (Vm) and pulsatility index (PI) will be recorded at each interval. Based on findings of TCD examinations, subjects will be placed into phenotypic groups.

Neurological exam: A focused neurological examination will be performed at admission, and at 0800 and 1600 daily (\pm 2 hours) while the patient is comatose (BCS \leq 2). A detailed neurological examination will be performed at each of the 1, 6, and 12 month (\pm 2 weeks) post-randomization follow-up visits. While hospitalized, the examination will focus on candidate neurological exam markers of increased brain volume: restriction or changes in eye movements, abnormal posturing (decerebrate, decorticate), changes in reflexes (corneal, gag, deep tendon). The follow-up neurological history and examinations will focus on determination of hard neurological abnormalities: tone, reflexes, movement, posture, interim unprovoked seizures, Neurological

development will be determined by administration of the Malawi Developmental Assessment Test or Kaufman Assessment Battery for children, depending on the age of the subject at the time of enrollment.

Brain swelling intervention: After brain MRI screening, subjects with severely increased brain volume scores (≥ 6) will be eligible for randomization. The parent/ caregiver will be approached for informed consent using the Randomization Consent document. If consent for randomization is granted, randomization assignment will be determined online or opening the next sequentially numbered sealed randomization envelope (stratified by malarial retinopathy status) and the subject's assignment to each of the three study arms determined.

Subjects may be randomized to:

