11.5 Sample Size and Power

For the primary outcome death/failure of the intervention, we conduct two parallel studies: (i) VENT versus control UC, (ii) HPS versus control UC. Approximately 128 children will be enrolled in the studies. This includes the 64 children in UC comprised of 16 randomized to UC in the 2018-2019 malaria seasons and augmented by 48 historical controls from previous seasons (2014-2017). We also randomized 16 children to VENT in the 2018-2019 malaria seasons.

Table 8: Summary of outcome measures and analytic plan		
Outcome measure	Outcome type/scale	Analytic method
PRIMARY OUTCOME		
Success of primary intervention or survival in the first 7 days after randomization	Binary	Logistic regression
SECONDARY OUTCOMES		
Brain volume determination (MRI on admission, then daily)	Ordinal	Ordinal regression
Optic Nerve Sheath Diameter (on admission, then daily)	Continuous	Linear regression. Serial assessments by repeated measures analysis
Transcranial Doppler ultrasound (on admission, then daily)	Continuous	Linear regression. Serial assessments by repeated measures analysis
Opening CSF pressure (mm CSF) (on admission)	Continuous	Linear regression
Heart rate variability patterns	Continuous	Linear regression. Serial assessments by repeated measures analysis
Neurologic exam * (on admission, then twice daily)	21 binary and 5 continuous variables	Linear or logistic regression
Papilledema (on admission, then daily)	Binary	Logistic regression
Severe neurologic sequelae at 16 and 12 months	Binary	Logistic regression. Serial assessments by repeated measures analysis
Hypotension that occurs within 30 minutes of sedation administration, initiation of mechanical ventilation or ventilator pressure adjustment.	Binary	Logistic regression.

Since the beginning of this study, we faced several logistical challenges but had success in recruiting 32 children in 2018-2019 (16 each in VENT and UC). Based on our current data, the estimated mortality in UC and VENT are respectively, 36% and 25%. Maintaining the mortality rate in UC, a one-sample lower test at significance level $\alpha=0.05$ of a null difference has 80% power to detect a reduction in mortality to 18% in VENT with 33 subjects in VENT.

[figure not shown]

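### Secondary Objective 2 promises validated biomarkers of brain swelling from one cohort, but the plan has about 31 candidates, no accuracy analysis against MRI and no control for selecting markers in the same children

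*Combined protocol and SAP*

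**What the plan says.** The Protocol Summary lists as Secondary Objective 2: "Among all children admitted to the Paediatric Research Ward and screened for eligibility for randomization, evaluate and validate biomarkers of increased brain volume". Section 3.1 states the objective again for a single group: "Among all children admitted to the PRW with CM whose parents consent to screening, evaluate and validate biomarkers of increased brain volume". The rationale (Section 2.3) repeats the intention, "we will test and validate other surrogate measures of increased brain volume", and also says that clinically reliable surrogates have not yet been found. Finding them and validating them are therefore both tasks for this cohort. The stated purpose is that, if an intervention works, "its implementation will not require MRI technology to identify subjects at high risk of death".

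The candidates appear in three places:

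- Section 3.2.2 lists, among others, "opening CSF pressure, archived samples of blood, urine and CSF. Daily while comatose: ophthalmoscopy for papilledema (present/absent), optic nerve sheath diameter in mm", plus NIRS and neurologic observations.
- Section 8.1 says the in-hospital examination targets "candidate neurological exam markers of increased brain volume".
- Table 8 gives the neurologic examination as "21 binary and 5 continuous variables" and adds optic nerve sheath diameter (ONSD), transcranial Doppler (TCD), opening CSF pressure, heart rate variability (HRV) and papilledema.

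Table 8 assigns each measure a regression type by scale. Section 11.7 describes generic linear, logistic, ordinal and repeated-measures models whose covariates include treatment arm, with 128 children expected across the three arms. Sections 11.7 to 11.7.2 contain no AUC, sensitivity, specificity or cut-off, no sample size for this objective, no hold-out set or resampling, and no multiplicity rule.

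**The concern.** Validation normally means that a marker, fixed in advance, is tested in children who played no part in choosing it. Here one cohort does both jobs. With many candidates, those that look best are partly those favoured by chance, and accuracy computed in the same children is biased upward.

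The stated models do not fill the gap. They treat the markers as outcomes and adjust for trial arm, which screened but unrandomised children do not have. No model relates a marker to the MRI score. The goodness-of-fit and residual checks in Section 11.7 do not address selection.

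The markers are meant to help identify high-risk children where there is no MRI. Overstated accuracy could send children without severe swelling to treatment and miss children who have it.

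**Working it through.** The plan gives no sample size, error rate or accuracy target for this objective, so it has no figure of its own to reproduce. The check asks what uninformative markers would look like if analysed without correction.

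**Inputs from the documents**
- Candidates in Table 8: 21 + 5 = 26 examination items, plus ONSD, TCD, opening pressure, HRV and papilledema = 31. This is a floor: NIRS is not in Table 8, and TCD and HRV each yield several parameters. Archived-sample assays are excluded because Section 2.3 defers them to later, separately funded work.
- Children with MRI (Section 4): 57 in 2018 and 42 in 2019, so 57 + 42 = 99. The 48 screened in 2020 had no brain volume assessment.
- Randomised in those two seasons: 8 + 24 = 32.

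**Assumptions**
- Two-sided 0.05 per marker.
- 99 children, 32 of them swollen. The number randomised is only a proxy for the number swollen. Larger samples of 150 (50 swollen) and 200 (70 swollen) were also tried.
- All markers uninformative: 22 binary at 30% prevalence and 9 continuous, with pairwise correlation 0, 0.3 or 0.6 on the underlying scale.

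**Chance of a false signal, independent markers**
- At least one of 31: 1 − 0.95^31 = 0.796.
- Expected number: 31 × 0.05 = 1.55.
- Two or more: 0.46 (binomial, 31 trials at 0.05).
- The 26 examination items alone: 1 − 0.95^26 = 0.737.
- Any one marker named in advance: 0.05.

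**Effect of correlation** (simulation, 99 children, 2,000 runs). The chance of at least one false signal is 82% at correlation 0, 73% at 0.3 and 58% at 0.6.

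**Apparent AUC when the true AUC is 0.50** (independent markers)

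| Children | Best single of 31, median | Score using all 31 | Same score, 10-fold cross-validated |
|---|---|---|---|
| 99 | 0.62 (95th percentile 0.68) | 0.85 | 0.50 |
| 150 | 0.60 | 0.78 | 0.50 |
| 200 | 0.585 | 0.74 | 0.49 |

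A separate simulation with 30 null markers gave 0.62 for the best single marker, 0.73 for a best-five model and 0.83 for all thirty at n = 100.

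**Which correction works** (30 null markers, 99 children)

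| Method | Best one | Best five | All thirty |
|---|---|---|---|
| Simple bootstrap optimism correction | 0.54 | 0.59 | 0.63 |
| Cross-validation, selection nested in each fold | 0.50 | 0.50 | 0.50 |

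The bootstrap removes only part of the bias when there are this many candidates for this few children.

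**The case against.** The strongest reply is that the plan describes no selection step. It never says that a best marker will be picked, a cut-off tuned or a combined score built, so the larger AUCs belong to analyses nobody has proposed. That is fair, and those figures are hypothetical. What remains is that the plan neither specifies nor excludes such steps while promising a validated result.

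The candidates are also not all equal. ONSD has earlier studies and ward data since 2013, TCD has prior literature and fixed phenotype criteria (Section 8.3.4), and NIRS has pilot data from the same ward (Section 2.1.12). New children can properly test a prior hypothesis about these. The concern falls mainly on the 26 examination items and on HRV, about whose evolution in cerebral malaria Section 2.3 says nothing is known.

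The simulation is a worst case: every marker is null, and the headline figure assumes independence. Posturing, reflexes and eye movements are probably correlated, which lowers the chance of a false signal but leaves it above one half at correlation 0.6.

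Finally, the clinical use is conditional on a successful intervention, and some passages speak only of potential surrogates. That limits the immediate harm but does not supply the missing analysis.

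**Conclusion.** The concern holds in a limited form. As written, the design cannot deliver validated biomarkers, because identification and validation share one cohort and the plan gives neither an accuracy analysis against MRI nor any control for selection.

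The size depends on assumptions. At two-sided 0.05 with all markers uninformative, at least one of 31 would look significant about 80% of the time if independent and about 58% at correlation 0.6. The best would show an AUC of about 0.62 with about 100 children. An uncorrected combined score, if one were built, could show about 0.83 to 0.85 from noise. The inflation shrinks as the number of children with MRI grows.

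A reader might infer that useless markers in general would emerge as validated. The documents do not support that. A given pre-named useless marker would pass only about 5% of the time, the best single null marker looks weak, and the plan sets no criterion by which anything would count as validated. This is a secondary objective, and the primary analysis is unaffected.

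**What to change.** In Section 11.7, add an analysis for Secondary Objective 2:

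1. Name the markers with earlier data (ONSD, TCD, NIRS) as pre-specified, stating the parameter to be used for each. Label the examination items and HRV as exploratory.
2. Report AUC, sensitivity and specificity against the consensus MRI score, at 6 or above versus below 6 (the randomisation threshold). Add 7–8 as a sensitivity analysis, since Section 8.3.2 ties those scores to the highest risk of herniation and death.
3. Estimate these by repeated cross-validation, with all marker selection and cut-off choice inside each fold. Simple bootstrap optimism correction should not be relied on here.
4. Use admission values for the main accuracy analysis, and keep the daily measures as repeated-measures analyses. Restricting to pre-treatment values would be ambiguous, because antimalarials start before the trial consents (Section 5.1).

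In Sections 2.3 and 3.1 and the Protocol Summary, describe this as internal validation.

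The cost is analysis code and wording, with no new data. The one downside is that reported accuracy will be less favourable.
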